**Figure 3.1-4: Detailed Study Schematic**

 Treatment beyond progression may be considered in select subjects as described in [Section 4.3.4](#).

 Diagnostic imaging must be performed every 8 weeks until disease progression, and in subjects who discontinue study treatment at the Investigator's discretion with a CR, PR, or SD via RECIST v1.1, imaging must be performed every 12 weeks until disease progression.

 For treatment visits in Parts B and C where BMS-986016 (relatlimab) and nivolumab are administered sequentially, nivolumab will be administered first over 30 minutes, followed by BMS-986016 administration within 15 to 30 minutes after completion of the nivolumab infusion. For doses of 960 mg relatlimab + 480 mg nivolumab Q4W, BMS-986016 infusion should be administered no sooner than 30 minutes following completion of nivolumab infusion.

 Note the 6-week DLT period will be initiated after completion of the 480 mg BMS-986016 dose level.

Note: As of Protocol Amendment 14, rechallenge is not permitted.

Assessments, including physical examinations, vital sign measurements, 12-lead electrocardiogram (ECG), and clinical laboratory evaluations, will be performed at selected times throughout the dosing interval. Subjects will be closely monitored for AEs throughout the study. Blood samples will be collected for up to 4 hours following the start of study drug administration for PK analysis.

Subjects will be allowed to continue on therapy until PD, clinical deterioration, or meeting criteria for discontinuation. Patients who discontinue treatment before 5 years will complete a 135-day clinical follow-up period, and a survival follow-up period for up to 5 years after the first dose. Patients who continue study treatment for longer than 5 years will complete a 135-day clinical follow-up period once the criteria for treatment discontinuation are met, but will not participate in a survival follow-up period. The study will end when all patients have completed their respective follow-up periods. Additional OS analysis may be conducted periodically until end of study.

### **3.1.1 Dose Escalation**

#### **3.1.1.1 Part A - Monotherapy**

In Part A, a 3 + 3 + 3 design will be used to assess the safety of BMS-986016 given as single agent. A fourth subject may be enrolled at the beginning of a dose escalation cohort following agreement between the Investigator and the Sponsor/Medical Monitor, if the subject is able to start the first day of dosing within approximately 1 week of the third subject in the same dose escalation cohort.

The dosages during dose escalation are provided in [Figure 3.1-1](#) and [Table 3.1.1.1-1](#).

Three subjects (or 4, if applicable) will initially be treated in each dose cohort; in Dose Cohort 1, each of the first 3 subjects (or 4, if applicable) will be designated as sentinel subjects and will begin treatment at least 5 days apart. Subjects in subsequent cohorts will not be required to observe the 5-day interval between treatment start dates.

Dose escalation in Part A will proceed as follows:

If 0 of the first 3 (or 4, if applicable) subjects experiences a DLT within the DLT evaluation interval, a new cohort of 3 subjects (or 4, if applicable) will be treated at the next higher dose level.

If 1 of 3 (or 4, if applicable) subjects experiences a DLT within the DLT evaluation interval, that cohort will be expanded to 6 subjects (or 7, if applicable).

If 2 of 6 (or 7, if applicable) subjects experience a DLT within the DLT evaluation interval, that cohort will be expanded to 9 subjects.

If  $\geq 2$  of 3 (or 4, if applicable),  $\geq 3$  of 6 (or 7, if applicable), or  $\geq 3$  of 9 subjects experience DLTs within a dose cohort during the DLT evaluation interval, then that dose level will be determined to have exceeded the MTD.

**Table 3.1.1.1-1: Dose Escalation and Dose Expansion Schedules for Part A and Part A1 BMS-986016 Monotherapy**

Part A Dose Escalation Cohort Number	Total Subjects	BMS-986016 Dose (IV; mg)
1	n = approximately 3-9	20
2	n = approximately 3-9	80
3	n = approximately 3-9	240
4	n = approximately 3-9	800
Total	N = approximately 12-36	
Part A1 Dose Expansion Cohorts		
NSCLC: prior anti-PD-1 or PD-L1 therapy allowed a	n = approximately 6-12	800
RCC: prior anti-PD-1 or PD-L1 therapy allowed a	n = approximately 6-12	800
Total	N = approximately 12-24	

a See [Section 3.3](#) for detailed eligibility criteria.

Prior to declaring the MTD (or MAD), and in consultation with Investigators, the Sponsor has the option to expand any cohort previously established to be safe in order to obtain additional experience or to investigate dose levels intermediate to those defined in the protocol. Dose escalation rules (cohort size, DLT evaluation interval, cohort expansion criteria, etc.) will apply to these expanded or additional cohorts. A maximum of 9 subjects will be enrolled in any additional or expanded dose cohorts.

No within-subject dose escalations will be permitted. If a dose level is found to exceed the MTD, subjects enrolled in that dose level may be treated at a lower dose following consultation and agreement between Investigators and the Sponsor.

### **3.1.1.2 Part B - Sequential Infusion**

Treatment in Part B will be initiated after the decision is made to escalate to the third dose cohort in Part A (in accordance with dose escalation rules). Subsequently, escalation in the 2 parts will

proceed in parallel. Treatment assignments for subjects eligible for both Part A and Part B will alternate between the 2 parts, with consecutively treated subjects assigned to different parts through interactive voice response system (IVRS) whenever possible. If there are no openings available in the part to which the subject would be assigned by this algorithm, then the subject will be assigned to the next open cohort or part.

As in Part A, a 3 + 3 + 3 design, or a BLRM-Copula design, as implemented in the site-specific amendment #15 (dated 13 August 2018) and superseding the 3 + 3 + 3 dose escalation design will also be used in Part B to assess the safety of BMS-986016 given in combination with nivolumab as a sequential infusion. A fourth subject may be enrolled at the beginning of a dose escalation cohort following agreement between the Investigator and the Sponsor/Medical Monitor, if the subject is able to start the first day of dosing within approximately 1 week of the third subject in the same dose escalation cohort. The potential dose levels evaluated during dose escalation are provided in Table 3.1.1.2-1. Intermediate and lower dose levels may be assessed following agreement between the Investigator and the Sponsor/Medical Monitor based upon ongoing review of safety data.

**Table 3.1.1.2-1: Dose Escalation Schedule for Part B — BMS-986016 in Combination with Nivolumab Q2W and Q4W**

Dose Cohort Number	Total Subjects	BMS-986016 Dose (IV; mg)	Nivolumab Dose (IV; mg)
Dose Escalation Schedule for Part B — BMS-986016 in Combination with Nivolumab Q2W Dosing			
1	n = approximately 3-9	20	80
2	n = approximately 3-9	20	240
3	n = approximately 3-9	80	240
Intermediate	n = approximately 3-9	160	240
4	n = approximately 3-9	240	240
Dose Escalation Schedule for Part B — BMS-986016 in Combination with Nivolumab Q4W Dosing			
1	n = approximately 3-9	160	480
2	n = approximately 3-9	240	480
3	n = approximately 3-9	320	480
4	n = approximately 3-12	480	480
5	n = approximately 3-15	960	480
6	n = approximately 3-15	1440	480
7	n = approximately 3-15	1600	480
Total	N = approximately 36-120		

Three subjects (or 4, if applicable) will be treated initially in each dose cohort; in Dose Cohort 1, each of the first 3 subjects (or 4, if applicable), designated as sentinel subjects, will begin treatment at least 5 days apart. Subjects in subsequent cohorts will not be required to observe the 5-day interval between treatment start dates.

In Part B, if the MTD is exceeded in Dose Cohort 2, the potential subsequent cohort will be treated with 80 mg BMS-986016 and 80 mg nivolumab. If this dose combination is found to be safe, following consultation and agreement between Investigators and the Sponsor, escalation may proceed at the previously defined BMS-986016 doses, maintaining the nivolumab dose at 80 mg, or an intermediate dose level. Testing of the Q2W and Q4W dosing schedules can proceed concurrently with independent escalation decisions based upon review of the current total safety experience and following consultation and agreement between Investigators and the Sponsor.

Prior to declaring the MTD (or MAD), and in consultation with Investigators, the Sponsor has the option to expand any cohort previously established to be safe in order to obtain additional experience or to investigate dose levels intermediate to those defined in the protocol. Dose escalation rules (cohort size, DLT evaluation interval, cohort expansion criteria, etc.) will apply to these expanded or additional cohorts. A maximum of 9 (or 15, in case of BLRM-Copula) subjects will be enrolled in any additional or expanded dose cohorts.

No within-subject dose escalations will be permitted. If a dose level is found to exceed the MTD, subjects enrolled in that dose level may be reduced to a lower dose following consultation and agreement between Investigators and the Sponsor.

### ***3.1.2 Cohort Expansion***

#### ***3.1.2.1 Cohort Expansion (Part A1) - Monotherapy***

The purpose of cohort expansion is to gather additional safety, tolerability, preliminary efficacy, PK, and pharmacodynamic information of BMS-986016 monotherapy. The doses selected for Part A1 will not exceed the MTD or MAD in Part A but may incorporate assessment of other data, including toxicities and PK and pharmacodynamic data from Part A. Doses to be considered may include doses intermediate to those evaluated in Part A, if recommended by the Investigators and the Sponsor. Two expansion cohorts will be restricted to the tumor types listed in [Table 3.1.1.1-1](#).

Subjects with PD in Part A1 may cross over to combination therapy with sequential infusion of nivolumab and BMS-986016 if the following criteria are met: 1) subject has confirmed disease progression (investigator-assessed RECIST v1.1-defined progression confirmed at least 4 weeks after the initial tumor assessment showing progression); 2) subject has not experienced BMS-986016-related AEs leading to permanent discontinuation; 3) subject is not continuing to derive any clinical benefit from BMS-986016 single-agent therapy as assessed by the Investigator; 4) the individual case has been discussed with the Medical Monitor prior to crossover; 5) at least an 8-week period between the last dose of monotherapy and the first dose of combination therapy. Subjects crossing over to combination therapy will start treatment at Cycle 1 Day 1 as described for subjects in Part C. Subjects who cross over will receive combination therapy in sequential infusion at the doses that have been declared safe in dose escalation and/or dose expansion parts at the time of crossover. The original protocol rules will apply accordingly. Combination therapy

may thus be administered for up to 12 additional 8-week cycles according to the protocol rules. Subjects who crossed over and subsequently have an objective response in combination therapy will not be considered in the decision making for Part C. Subjects in Part C cannot cross over to Part A1.

Collection of archival tissue (baseline) and tumor biopsies (baseline and on-therapy) will be optional in subjects crossing over, and PK and biomarker monitoring will be limited ([Sections 5.5](#) and [5.7](#)).

### **3.1.2.2 *Cohort Expansion (Part C) - Sequential Infusion***

The purpose of cohort expansion is to gather additional safety, tolerability, preliminary efficacy, PK, and pharmacodynamic information in subjects treated with sequential infusion of nivolumab followed by administration of BMS-986016. The initial doses selected for specific Part C cohorts will not exceed the MTD (or MAD if no MTD is determined) in Part B but may incorporate consideration of other data, including (but not necessarily limited to) toxicities, PK, and pharmacodynamic data from Parts A and B and can be chosen while additional Part B dose escalation cohorts continue to be explored. Part C expansion cohort doses to be considered will include those doses shown to be safe in Part B (or intermediate to those doses) as recommended by the Investigators and the Sponsor. Dosing of subsequent patients within an expansion cohort, or between cohorts, can be increased (if deemed safe in Part B) or decreased (based upon ongoing reviews of the totality of the safety data), all to be decided in agreement between the Investigators and the Sponsor. There will be no dose adjustments for individual subjects. Expansion cohorts in Part C will be restricted to 7 tumor types in 8 cohorts ([Section 3.1](#)). Efficacy analyses in all cohorts will be guided by a multistage evaluation approach. Cohorts deemed futile at Stage 1 will be discontinued, whereas those deemed promising may be expanded up to 90 to 120 subjects in total after careful evaluation of all available data, including the totality of efficacy, safety profile, and PK/pharmacodynamics ([Section 8.1.2](#)). Otherwise, additional subjects may be treated to collect more data during Stage 2 in order to make a decision for further expansion. Enrollment to Stage 2 or further expansion in a given cohort can continue even if the other cohorts are still in Stage 1. Subjects who crossed over to combination therapy in Part A1 and subsequently have an objective response will not be considered in the decision making for Part C. Subjects in Part C cannot crossover to Part A1 either.

### **3.1.2.3 *All Cohort Expansion Parts (A1, C, D, and E)***

Continuous evaluation of toxicity events in the cohort expansions will be performed throughout enrollment in the expansion cohorts. **Not applicable as per Protocol Amendment 14:** Safety conference calls with the BMS Medical Monitor, Investigators, and representatives of the Sponsor are being held regularly during conduct of the study. In addition, separate BMS Medical Safety Teams routinely review safety signals across the BMS-986016 and nivolumab programs. If, at any time, the aggregate rate of treatment-related toxicities meeting DLT criteria exceeds 33% across all subjects treated in any of these cohort expansions, the findings will be discussed and further enrollment must be interrupted in that particular cohort and other relevant cohorts. Depending on the nature and grade of the toxicity and after assessing the benefit-risk ratio, a new dose(s) for all

cohorts may be initiated at a previously tested lower dose level or at a dose level intermediate to previously tested lower dose levels.

### **3.1.2.4 *Rechallenge in Dose Escalation (Parts A and B) and Cohort Expansion Parts (A1, C, D, and E)***

If, after discontinuing study treatment at the Investigator's discretion, subjects progress during the Clinical Follow-up period or the Survival Follow-up period, subjects could further receive therapy with BMS-986016 alone or in combination therapy (**Rechallenge**) as long as the benefit-risk ratio is considered favorable by the Investigator and the Medical Monitor and the following eligibility criteria are met: 1) subject has confirmed disease progression (Investigator-assessed RECIST v1.1-defined progression confirmed at least 4 weeks after the initial tumor assessment showing progression); 2) subject has not experienced BMS-986016-related AEs leading to permanent discontinuation. The rechallenge-eligible Survival Follow-up may continue for up to 5 years from the first dose of study drug. The original dose and schedule of therapy and protocol rules will apply. For the rechallenge, collection of archival tissue (baseline) and tumor biopsies (baseline and on-therapy) will be optional and PK and biomarker monitoring will be limited ([Sections 5.5](#) and [5.7](#)). **As of Protocol Amendment 14, rechallenge is not permitted.** All subjects who discontinue primary study treatment following implementation of Protocol Amendment 14 will not be eligible for rechallenge. Subjects currently receiving rechallenge treatment will be allowed to continue, and subjects currently in the rechallenge-eligible Survival Follow-up as of this protocol amendment remain eligible for rechallenge.

Subjects who are rechallenged and who subsequently have an objective response will not be included in the primary analysis of efficacy. Responses to rechallenge will be evaluated in a separate analysis. Subjects will not be rechallenged a second time.

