Tumor status will be assessed at baseline during treatment (every 8 weeks regardless of dose delays) during the Treatment period. Tumor assessments will continue every 12 weeks during the Clinical Follow-up and Survival periods until disease progression in subjects who discontinue study treatment, at the Investigator's discretion, with CR, PR, or SD by RECIST v1.1. CT and MRI scans will be read and assessed locally per RECIST v1.1. All imaging scans must be de-identified and archived in their native DICOM format as part of the subject's study file. At the Sponsor's discretion, scans may be collected centrally to be reviewed by independent radiologists.

Efficacy assessment of subjects who have been rechallenged after achieving a response or SD will be conducted in a separate analysis. Scans for participants who are rechallenged should be performed as per the on-treatment schedule in [Table 5.1-2](#) and submitted to the central imaging vendor for collection. However, the BOR in the first treatment may be considered in the study analysis. Subjects who cross over from BMS-986016 monotherapy (Part A1) to combination therapy are not to be included in the analysis of any expansion cohorts with combination therapy. **As of Protocol Amendment 14, rechallenge is not permitted.**

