## **8.2            *Populations for Analyses***

**All Enrolled Subjects Analysis Set:** This analysis set contains all subjects (including screen failures) who signed an ICF for the study.

**All Treated Subjects Analysis set:** This analysis set includes all subjects who receive either drug.

**Response-evaluable Subjects:** This analysis set includes all subjects who receive either study drug, have a baseline tumor assessment with measurable disease, and 1 of the following: 1) at least 1 evaluable on-treatment tumor assessment, 2) clinical progression, or 3) death prior to the first on-treatment tumor evaluation.

**Enriched Subjects:** This analysis set includes all treated subjects with LAG-3 expression.

**BMS-986016 Pharmacokinetic Analysis Set:** This analysis set includes all subjects who receive BMS-986016 and have at least 1 valid PK parameter to be included in statistical analyses of BMS-986016 PK data.

**BMS-986016 Immunogenicity Analysis Set:** This analysis set includes all subjects who receive BMS-986016 and have baseline and at least 1 postbaseline preinfusion BMS-986016 immunogenicity assessment.

**Nivolumab Immunogenicity Analysis Set:** This analysis set includes all subjects who receive nivolumab and have baseline and at least 1 postbaseline preinfusion nivolumab immunogenicity assessment.

**Pharmacodynamic Analysis Set:** This analysis set includes all treated subjects for whom pharmacodynamic measurements are available at baseline and at least 1 other time point.

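### The rechallenge rule, as written, drops subjects from the primary efficacy analysis because they later respond, and it conflicts with Sections 5.4.2 and 8.3.1

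*Combined protocol and SAP*

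**What the plan says.** **Rechallenge section (3.1.2.4, repeated in the synopsis).** "Subjects who are rechallenged and who subsequently have an objective response will not be included in the primary analysis of efficacy". The next sentence is about responses, not subjects: "Responses to rechallenge will be evaluated in a separate analysis". Entry to rechallenge requires "Investigator-assessed RECIST v1.1-defined progression confirmed at least 4 weeks after the initial tumor assessment showing progression".

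**Efficacy assessment (5.4.2).** "Efficacy assessment of subjects who have been rechallenged after achieving a response or SD will be conducted in a separate analysis". This covers every subject rechallenged after a response or stable disease, whatever rechallenge achieves. It continues: "However, the BOR in the first treatment may be considered in the study analysis". Rechallenge scans are to be "submitted to the central imaging vendor for collection".

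**Endpoints and populations (8.2, 8.3.1, 8.4.2).** Section 8.3.1 divides ORR and DCR by all treated subjects in the population of interest. It closes BOR at first documented progression or at subsequent therapy, whichever is earlier. The enriched set in Section 8.2 is equally inclusive: "This analysis set includes all treated subjects with LAG-3 expression". Neither Section 8.2 nor Section 8.4.2 mentions a rechallenge exclusion.

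**Assessor.** The Part D1-Q2W coprimary ORR is by BICR (8.3.1), and Section 5.4.3 makes BICR the primary assessment where applicable. Rechallenge entry rests on the Investigator's reading.

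**The concern.** An analysis set should not depend on an outcome observed after the endpoint has been fixed. By the Investigator's assessment, a subject's first-course BOR is settled before rechallenge starts. Removing that subject because the second course succeeded conditions the primary analysis on later success. The direction of the bias depends on who is removed: a first-course responder leaves both numerator and denominator, and a stable-disease subject leaves only the denominator.

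The sections also cannot all be followed. Section 3.1.2.4 removes rechallenge responders, Section 5.4.2 separates all subjects rechallenged after a response or stable disease, and Section 8.3.1 removes nobody. The permissive wording about first-course BOR leaves the choice open in an open-label study, where it could be made with outcomes known.

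**Working it through.** **Inputs.** n = 90 LAG-3-positive subjects and a descriptive target that the 95% interval exclude 10% (Section 8.1.4.1); Clopper-Pearson intervals (Section 8.4.2). The number of affected subjects, k, is not in the documents; k = 0 to 4 is assumed.

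**Formula.** For x responses in n, the lower limit is the 2.5% quantile of Beta(x, n − x + 1) and the upper limit is the 97.5% quantile of Beta(x + 1, n − x).

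**Step 1: reproduce the plan's figure.** For 16/90, the 2.5% quantile of Beta(16, 75) is 10.52% and the 97.5% quantile of Beta(17, 74) is 27.26%. Table 8.1.4.1-2 prints 10.5% and 27.3%. For 15/90 the lower limit is 9.64%, so 16 is the smallest count at n = 90 that excludes 10%.

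**Step 2: remove k first-course responders who respond again,** giving (x − k)/(n − k).

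| Start | k | Result | ORR | Lower limit |
|---|---|---|---|---|
| 16/90 | 0 | 16/90 | 17.8% | 10.52% |
| 16/90 | 1 | 15/89 | 16.9% | 9.75% |
| 16/90 | 2 | 14/88 | 15.9% | 8.98% |
| 18/90 | 0 | 18/90 | 20.0% | 12.31% |
| 18/90 | 2 | 16/88 | 18.2% | 10.76% |
| 18/90 | 3 | 15/87 | 17.2% | 9.98% |
| 20/90 | 0 | 20/90 | 22.2% | 14.13% |
| 20/90 | 4 | 16/86 | 18.6% | 11.02% |

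One removal crosses 10% from 16/90. From 18/90 it takes three. From 20/90, four do not suffice.

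**Step 3: remove k first-course stable-disease subjects who respond to rechallenge,** giving x/(n − k). Starting at 15/90 (9.64%), k = 1, 2, 3 and 4 give 9.75%, 9.87%, 9.98% and 10.10% (15/86). The estimate rises, and crosses 10% only at k = 4.

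**Step 4: the same data under each section.** Assume 16 first-course responders; one of them and four stable-disease subjects are rechallenged, and only that responder responds again.
- Section 8.3.1: 16/90, lower limit 10.52%.
- Section 3.1.2.4 read literally: 15/89, 9.75%.
- Section 5.4.2, if first-course BOR is not used: 15/85, 10.23%. If it is used, the result is again 16/90.

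**Step 5: what rechallenge does to BOR, PFS and DOR.** By Investigator assessment, the progression required for rechallenge has already closed BOR (8.3.1) and is already the PFS and DOR event (8.3.1, 8.3.2.2). Nothing is undefined there. By BICR, a subject may have no progression on record at the first rechallenge dose. Sections 8.3.1 and 8.3.2.2 do not say whether rechallenge is then subsequent therapy. So the closing date of the BICR BOR window is not stated, nor is the treatment of a later progression or death in BICR PFS and DOR.

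**The case against.** **Intent.** The sentence after the exclusion concerns responses to rechallenge, so the authors probably meant to leave out the response and keep the subject. Section 5.4.2 allows first-course BOR to be used, and that fits Section 8.3.1. This is fair as a reading of intent, and the 15/85 case rests on the less natural reading. But the controlling sentence, in two places, excludes subjects, and nothing in the text corrects it.

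**Size.** The illustrations sit near the threshold. The upward one needs four stable-disease subjects to respond after progressing. If the Part C rates in Section 1.1.6 are borrowed as an assumption, four responses would be expected from about 4/0.182 = 22 rechallenged subjects (LAG-3-positive rate) or 4/0.115 = 35 (overall rate), out of 90. The 10% target is descriptive, and Sections 1.2 and 8.5 disclaim formal hypotheses and inference. Enrollment has closed and Amendment 14 ended new rechallenge eligibility. All of this stands and limits the practical effect. Subjects already on rechallenge or already eligible remain, and existing data still need one rule.

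**Stronger readings a reader might infer.** One is that the plan is silent on how rechallenge affects BOR, PFS and DOR. It is not: for Investigator-assessed endpoints the entry criterion settles the matter, and only the BICR case is open. Another is that a rechallenge response could be counted in the primary ORR. Section 3.1.2.4 sends such responses to a separate analysis, Appendix 2 runs BOR only to the end of treatment, and Section 5.4.2 sends the scans for collection without saying that BICR reads them.

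**Conclusion.** The point holds in limited form. As written, the synopsis and Section 3.1.2.4 make an outcome-dependent exclusion from the primary efficacy analysis, in conflict with the all-treated denominator in Section 8.3.1 and with the different group and optional first-course BOR in Section 5.4.2. If followed literally, the exclusion can bias ORR in either direction. One affected subject is enough to change the reading at 16/90 (10.52% to 9.75%); it takes three at 18/90, and four do not change it at 20/90. These figures assume the number affected, and they matter only if the literal rule is applied and the result lies near 10%. If Section 8.3.1 is followed, the exclusion effect does not arise.

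The BICR point is secondary: it concerns only subjects with no BICR progression before rechallenge. The text should be corrected, but the sample size and interval method are not in question.

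**What to change.** 1. In the synopsis and Section 3.1.2.4, replace the exclusion sentence with: *All treated subjects remain in the primary efficacy analysis with their first-course BOR; responses to rechallenge are not counted in BOR, ORR, DCR or DOR and are reported separately.*
2. In Section 5.4.2, make the subject of the separate-analysis sentence *Assessment of responses to rechallenge*, and change the permissive wording on first-course BOR to *will be used*.
3. In Section 8.3.1, state that where BICR has not called progression before rechallenge, the BICR BOR window closes at the first rechallenge dose. This matches the apparent intent of Section 3.1.2.4.
4. State how BICR-based PFS and DOR treat progression or death after rechallenge in those subjects. Statisticians would differ on whether to censor or to keep following, so the choice is the sponsor's; it needs only to be written down.

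The cost is one sentence in two places, two phrases in Section 5.4.2, and short additions to Sections 8.3.1 and 8.3.2.2. No new data are needed, and rechallenge eligibility and treatment are untouched.
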